Detailed Protocol Title: Behavior and brain responses to drugs

NCT03964350 Unique Protocol ID: IRB19-0293

Date: 4/11/22

Detailed Protocol Title: Behavior and brain responses to drugs Date: Investigators: [name] Other personnel:

IRB19-0293

Summary: Alcohol abuse and dependence remain significant public health issue, and there is a need to identify risk factors predicting excessive alcohol use. We and others have demonstrated individuals vary widely in their responses to an acute dose of alcohol: Some people experience mainly stimulant-like effects which are generally considered pleasurable, whereas others experience sedative-like effects which are rated more negatively (Holdstock and [name], 1998; King et el 2011). Moreover, the stimulant-like responses to alcohol appear to be predictive of an escalation in use (King 2016). An important question is whether the patterns of stimulant-like and sedative-like subjective effects correspond to differences in brain activation with the drug. We (Weafer et al, 2018) recently reported a good correspondence between stimulant-like subjective response to intravenous alcohol (0.8 g/kg) and activation of ventral striatal brain areas. In the present project, we wish to extend these interesting findings in two ways: i) to examine the dose-relationships between the mood-brain correlations by administering placebo and two doses of alcohol (0.4 and 0.8 g/kg), ii) to investigate the relationship when the drug is administered by the more naturalistic oral route. We propose to assess brain activation patterns in relation to subjective effects using fMRI in a counterbalanced, 3-session, placebo-controlled, double-blind, within-subjects design with placebo, 0.4 g/kg alcohol and 0.8 g/kg alcohol. During an initial drug challenge screening session, 50 potential scanning subjects will receive a single dose of 0.8 g/kg alcohol, to identify individuals who exhibit a pronounced stimulant effect (N=15) or a sedative effect (N=15) from the drug, and only these will participate in the two scanning sessions. We hypothesize that individual variation in the self-reported stimulant or sedative-like effects of alcohol will correspond with variation in activation patterns in reward-related brain regions.

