number of subjects. More recently, a study used fMRI to show that oral alcohol suppressed brain activity during performance of simple cognitive tasks (Horn et al. 2006). However, few studies have examined the localized effects of alcohol in the brain in relation to its self-reported subjective effects. As noted above, we recently (Weafer et al, 2018) examined fMRI BOLD response after intravenously administered alcohol. As expected, we found that alcohol produced stimulant-like effects in a subset of individuals, and using region of interest analyses we showed that the time course of stimulation correlated with BOLD signal in the striatum. In the present study we aim to extend this finding i) using more naturalistic, oral administration of ethanol, ii) using two different doses of alcohol, and iii) adding ASL measures to monitor changes in blood perfusion to inform interpretation of neural activation changes. We hypothesize that inter-individual variation in the self-reported subjective effects are expected to be associated with increases in the mesolimbic system (related to dopamine activity), whereas sedative-like effects are expected to be more associated with areas rich in GABA.

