Design: We will measure individual differences in brain activity after two doses of alcohol (0.4 g/kg, 0.8 g/kg) or placebo using fMRI. Participants (N=50) will first be pre-selected ('ascertained') based on their responses to a single dose of alcohol (0.8 g/kg) in the behavioral laboratory. Individuals who exhibit either a clear stimulant-like response or a clear sedative-like response to alcohol will be invited to continue to the three fMRI scanning sessions. From the 50 participants tested, we will select 15 stimulant responders and 15 sedative responders. The three imaging sessions will be at least 72 h apart. At each session, subjects will receive the beverage containing alcohol or placebo, and then be placed in the fMRI scanner. Order of the three drug conditions (0, 0.4 and 0.8 g/kg ethanol) will be randomized and the drug will be administered under double-blind conditions. Immediately before and after the scan, subjects will complete standardized questionnaires to assess mood and subjective drug effects. We hypothesize that stimulant-like subjective effects will be associated with increases in activation in the striatum and regions related to the mesolimbic dopamine circuit. To minimize variability related to body composition and cycle phase, only males will be recruited for this preliminary study. Later, we will extend the study to include female participants.

Subject Recruitment and Screening

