from the TLFB as a covariate. Based on previous associations between subjective alcohol response and striatal activity, we focused our analyses within three hypothesis-driven anatomically-focused bilateral striatal regions of interest (ROIs): the nucleus accumbens, caudate, and putamen. We also included bilateral primary visual cortex to serve as a negative control ROI. The striatal ROIs were defined via the AAL atlas and created using MARINA (www.bion.de/eng/MARINA.php; Walter *et al*, 2003). The primary visual cortex ROI (Brodmann area 17) was created using the WFU PickAtlas tool (Maldjian *et al*, 2004; Maldjian *et al*, 2003). We extracted parameter estimates/ β weights representing the correlation between BOLD signal and subjective ratings in z-scores from each ROI following alcohol and placebo and conducted paired *t*-tests in SPSS to compare the two drug conditions. We applied a Bonferroni correction across the four ROIs tested, and so the p-value was set at p < 0.0125. We also conducted exploratory, whole-brain analyses of correlations between BOLD signal and stimulation and sedation ratings using SPM12 (cluster-forming voxel-wise height of *p* < 0.001, *k* = 50). Statistical inferences were based on cluster level significance, corrected for family wise error (FWE, *p* < 0.05).

ASL Analysis

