ASL data will be acquired using a pseudo-continuous sequence (TR = 4700 ms, voxel size= 3.4x3.4x5mm, FOV = 220x220x145mm, flip angle = 90 degrees, TE = 13 ms, bolus time = 1800 ms, TI = 3600 ms) with 35 control-label pairs. A proton density (PD) image (TR = 10000 ms, TE = 13 ms, voxel size = 3.4x3.4x5mm) will be acquired and used as a calibration image for cerebral blood flow (CBF) quantification in addition to the T1-weighted structural scan used for registration. Data will be preprocessed and analyzed using FSL analysis tools (Smith et al., 2004). Each data set will be preprocessed using a pipeline including motion correction, registration of ASL to the structural image, partial volume correction and distortion correction. Quantification of CBF will be completed using FSL's BASIL tool (Chapell et al., 2009). CBF will be quantified in units of ml/100g/min using a kinetic model and defaults for the parameters consistent with the formula in the ASL consensus paper (Aslop et al., 2015). For group analysis, quantified CBF images will be normalized to MNI space, smoothed and adjusted to account for individual differences in global CBF and voxelwise within-group ANOVAs will be conducted to assess for drug effects. Voxels showing differential perfusion will be converted to masks and used to interpret drug effects found from fMRI analyses.

Dependent Measures:

• **Subjective Effects.** Participants will complete comprehensive subjective effects questionnaires during the initial baseline session to determine their subjective alcohol profile. They will complete the three questionnaires described below at 15-30 min intervals during the baseline session. During the scanning sessions they will complete only the 5 questions of the DEQ (below) at 5 min intervals.

Biphasic Alcohol Effects Scale (BAES; Martin et al, 1993): 14-item questionnaire on which subjects rated the degree to which they feel subjective stimulant and sedative responses to alcohol on 11-point likert-type scales.

Subjective Effects of Alcohol Scale (SEAS; Morean et al, 2013): also a 14-item questionnaire on which subjects rated the degree to which they feel subjective stimulant and sedative responses to alcohol on 11-point likert-type scales.

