The minimal risks to subjects are justified by the knowledge to be gained. The findings will be important from a basic science perspective. The data will help us to elucidate the neural substrates of alcohol-induced subjective effects and how these vary between individuals which might determine individual susceptibility to alcohol abuse and dependence.

Confidentiality: Screening information and subjective and physiological data will remain in the lab at all times, and will only be accessible to personnel directly related to the study. Subjects will be identified only by assigned code numbers in all analyses, and publication of results will not identify any subjects by name. Data will not be shared unless a qualified scientist expressly requests it for re-analysis or verification purposes. In this event, no subject names will be included in shared data, only code numbers.

Recruitment and informed consent: Subjects will be recruited from the university and surrounding community by posters, advertisements in the student newspaper, and word-of-mouth referrals. At the time of the initial screening interview and again during the orientation session preceding the study subjects will be required to read the consent form and may ask any questions they may have about it. After the study has been fully explained and questions have been answered by the Principal Investigator or post-doctoral Research Associate, and before the first session, the subject will sign the consent form. The consent form outlines the procedures to be followed. Subjects agree in the consent not to take other drugs for 24 hours before and 12 hours following each session, and not to operate any machinery requiring concentration for 12 hours following the sessions. Subjects will be informed that blood alcohol (BAL) levels and urine samples will be obtained before each session.

Summary

We propose to compare responses to acute oral doses of ethanol in healthy young adults who experience mainly stimulant subjective effects from the drug (N=15) or mainly sedative effects (N=15). To identify stimulant and sedative responders we will first administer a single dose of alcohol (0.8 g/kg) to 50 healthy adults to characterize their responses. From the 50 subjects who complete this initial session we will select 15 stimulant responders and 15 sedative

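### The between-person hypotheses and the promised stimulant-versus-sedative comparison have no planned test; the BOLD tests address within-man coupling only

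*Combined protocol and SAP*

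**What the plan says.** Two hypotheses are worded across people. The opening Summary expects that "individual variation in the self-reported stimulant or sedative-like effects of alcohol will correspond with variation in activation patterns in reward-related brain regions". The Background expects that "inter-individual variation in the self-reported subjective effects are expected to be associated with increases in the mesolimbic system", and links sedative-like effects to GABA-rich areas. The closing Summary sets the matching design aim: "We propose to compare responses to acute oral doses of ethanol in healthy young adults who experience mainly stimulant subjective effects" with those who experience mainly sedative effects, 15 men in each group.

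Other statements can be read within persons. The opening Summary aims to study dose relationships in mood-brain correlations, and Design expects that "stimulant-like subjective effects will be associated with increases in activation in the striatum".

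Under fMRI Data Acquisition and Analysis, each man's BOLD signal is correlated over time with his own ratings, and the coefficient is Fisher-transformed. The ROI endpoint is a value "representing the correlation between BOLD signal and subjective ratings in z-scores from each ROI following alcohol and placebo". It is compared between alcohol and placebo by paired t-test in four ROIs at p < 0.0125. The exploratory whole-brain analysis also concerns BOLD-rating correlations. The only person-level covariate is drinks per week.

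Under ASL Analysis, "CBF will be quantified in units of ml/100g/min using a kinetic model". These images are adjusted for global CBF, tested by within-group ANOVA for drug effects, and used as masks to interpret the BOLD results.

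**The concern.** Screening 50 men to select 15 from each end of the response range serves a question about differences between men. The planned tests ask something else: whether BOLD follows a man's ratings over time more closely after alcohol than after placebo, on average over men. That mean can be clearly positive when stronger responders activate no more than weaker ones. It can be near zero when they activate much more.

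At stake is interpretation. A significant paired test could be read as support for the between-person hypothesis, which it does not address. A real association between men, or a real difference between responder groups, would have no pre-specified test.

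**Working it through.** **1. Reproducing the plan's figure.** 0.05/4 = 0.0125, the stated ROI threshold. The documents give no power calculation, so N = 30 cannot be reproduced. Two-sided testing is assumed throughout.

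**2. Matching questions to tests.**

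| Question | Level | Planned test |
|---|---|---|
| Mood-brain correlation (opening Summary, aim i; Design) | within person, on one reading | paired t on Fisher z |
| Individual variation in effect and activation (opening Summary, Background) | between persons | none written |
| Stimulant versus sedative responders (closing Summary) | between groups | none written |
| Drug effect on perfusion (ASL Analysis) | within person | within-group ANOVA |

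**3. What the planned test responds to.** Inputs from the documents: 30 men; 60-min scan with ratings every 5 min, so 60/5 = 12 points; effect expected to peak within 20 min; alpha 0.0125. The rest is assumed:
- Each man has a rating amplitude S and a BOLD amplitude A, both with SD 1 and with correlation rho between men.
- Each alcohol series is 2 × amplitude × g(t) + noise (SD 1). The shared curve g(t) peaks at 20 min and then declines.
- Placebo series are noise only.
- The CBF-like measure is A + noise (SD 0.5).

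The planned test is a paired t on Fisher z. The comparator is the correlation across men of the CBF-like measure with the rating difference. Percentage of 1,500 runs rejecting at 0.0125:

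| Mean amplitude of S and A | Planned: rho = -0.6 / 0 / +0.6 | Between-man: rho = -0.6 / 0 / +0.6 |
|---|---|---|
| 2 SD | 99.6 / 99.8 / 99.9 | 66.1 / 1.1 / 68.3 |
| 1 SD | 5.1 / 23.6 / 54.1 | 68.1 / 1.1 / 67.0 |
| 0.5 SD | 3.3 / 2.3 / 18.3 | 66.3 / 1.3 / 66.5 |
| 0 | 10.5 / 0.9 / 9.1 | 69.1 / 1.5 / 68.6 |

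Down a column of the planned test, rho is fixed and the result still moves with the mean effects. In the top row it cannot tell a positive association from none or a reversed one.

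**4. Limiting case.** If activation differs between men but is steady within the scan, a separate simulation (4,000 runs, n = 30, r = 0.4 to 0.6) has the planned test rejecting in 1.1-1.6% of runs, about its nominal 1.25%.

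**5. Precision of a between-man test at 0.05/3 = 0.0167.** The detectable correlation is r = tanh[(z₁₋α/₂ + z₀.₈)/√(N-3)].
- N = 30: tanh[(2.394 + 0.842)/√27] = tanh(0.623) = 0.55.
- N = 24 (assumed; dropout is expected but no rate is given): tanh(3.236/√21) = tanh(0.706) = 0.61.
- Power at N = 30 is Φ(atanh(r)·√27 - 2.394): r = 0.4 gives Φ(2.201 - 2.394) = 42%; r = 0.5 gives 68%; r = 0.6 gives 89%.
- A 15 versus 15 contrast (noncentral t, 28 df, noncentrality d·√(15/2)) has 80% power at d = 1.25.

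**6. Pooling both doses.** If alcohol-minus-placebo differences at both doses enter one model without a dose term, dose raises both variables and produces a slope without any between-man association. Two simulations under different assumed dose effects rejected in 18-31% and 46-85% of runs at 0.05/3. With a dose term the rate was about 1-3%.

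**7. ASL timing.** 35 pairs × 2 × 4.7 s = 329 s, about 5.5 min per run. The number of runs and their place in the 60-min scan are not stated.

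**The case against.** A reader might infer that the trial's hypothesis is never tested. That is too broad. The aim about mood-brain correlations and the hypothesis under Design can be read within persons, and the Background presents the intravenous-alcohol result that this trial extends as a time-course correlation. The Fisher-z test addresses that reading.

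A reader might also infer that the planned test is blind to a between-man association, rejecting only at its nominal level. That needs activation to be steady within the scan, whereas the protocol expects a peak within 20 min. With a shared time course and mean effects of 1 SD, rejection rises from 24% at rho = 0 to 54% at rho = 0.6. The test is sensitive to the association but not specific to it.

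Nor does a man's z carry no information on the size of his response. A correlation is unchanged when a whole series is rescaled, but with fixed noise z rises with amplitude; simulated correlations between the two were about 0.4 to 0.57, depending on the assumptions. A group contrast in z is therefore worth having, although it is not a measure of activation.

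Three further points stand. The analysis plan refers to a previous study that cannot be checked here. ASL is included to help interpret the BOLD results, and its global adjustment limits any test to regional perfusion. The documents call the study preliminary and a pilot, and an added test would itself often miss a moderate association. None of these supplies the missing between-person test.

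**Conclusion.** The point holds in a limited form. The between-person hypotheses of the opening Summary and Background, and the responder comparison of the closing Summary, have no written test. The paired Fisher-z tests answer a within-person question and cannot settle the between-person one.

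The gap in the plan follows from its text. The rejection rates depend on assumed amplitudes, noise and time course, and show only that mean effects and association are mixed. The whole-brain analysis is briefly described and is read here as using the same within-man maps. For a pilot, this should be fixed; the documents do not support treating it as a fatal flaw.

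**What to change.** 1. Describe the paired Fisher-z tests as tests of within-man coupling.
2. Pre-specify a between-man test for each striatal ROI at 0.05/3. Options are the stimulant-versus-sedative contrast (group by dose) in ROI CBF and in Fisher z, and a regression of alcohol-minus-placebo ROI CBF on the same man's alcohol-minus-placebo in-scan rating on the lively/talkative item. Name the one that carries the conclusion, because 0.05/3 covers three regions for one test only.
3. If both doses enter one mixed model, include a dose term and separate the between-man slope from the within-man slope.
4. Do the same for the relaxed/sluggish item as the sedative hypothesis, in regions named in advance.
5. State when ASL is acquired, use ratings from that window, and say that the test concerns regional perfusion after global adjustment.
6. For the group contrast, use one definition of responder. Experimental Procedure selects on the two alcohol-effect scales, and the closing Summary selects on Arousal from a mood questionnaire.

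The cost is analysis-plan wording and a few models on measurements already planned, plus a decision on ASL timing. No visits or participants are added. State the downside: 80% power needs r of about 0.55 with 30 men, or about 0.61 with an assumed 24 completers, and power at r = 0.4 is about 42%. Because men are chosen from the extremes, r should not be reported as a population value.
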